## Abstract

### **Objective(s) and Hypotheses:**

The aging Veteran population, together with high exposure to Agent Orange or other herbicides during military service, has made diseases such as Parkinson's disease (PD), currently affecting more than 80,000 Veterans, a major health issue in the Veterans' health system. Mobility and cognitive limitations are a common problem in PD and are associated with significant disability, increased fall risk, reduced quality of life, and increased caregiver burden. While less is known about its benefit on cognition, physical therapy has proven to be an effective treatment to mitigate mobility limitations, though the response to rehabilitation interventions is highly variable. The proposed research will inform our understanding of the impact of certain genetic profiles associated with learning impairments on motor and cognitive benefits in response to gait rehabilitation, and will provide an important foundation for more personalized and improved gait rehabilitation programs for different subgroups of PD patients.

The long-term goals of this research are: (Aim 1) to determine if certain genetic variants associated to learning impairments impact the motor and cognitive benefit experienced in response to physical rehabilitation in Veterans with Parkinson's disease (PD), and (Aim 2) to use that knowledge to identify subpopulations of patients that may require rehabilitative strategies tailored to their genotype to optimize physical rehabilitation.

### **Research Design:**

To achieve these goals we will enroll 30 Veterans with PD (10 in each of the genotype groups carriers of BDNF-Met66, carriers of APOE-ε4 (N=10) and those not carrying either of those variants) in a 10-week moderate intensity gait training program consisting of 2 times per week treadmill training with verbal cues for gait quality. Aim 1 will examine the association between variants in 2 genes known to affect cognition and motor learning (APOE-ε4 and BDNF-Met66), and motor improvements after gait training. Aim 2 will examine the effect of APOE-ε4 and BDNF-Met66 genetic variants on cognitive changes in response to this training program.

### **Methodology**

For Aim 1 we will sensitively and objectively assess changes in walking form, during and after training using state-of-the-art quantitative gait analysis, and compared between three genotype groups.

For Aim 2 we will measure cognitive performance pre- and post-training using a brief, targeted battery aimed at assessing attention, processing speed, executive function, and learning/memory, the domains more affected, and more likely to improve with physical exercise in PD.

### **Relevance to VA Mission**

The results of this project will enhance our knowledge regarding the influence of different genetic profiles in the response to physical rehabilitation in Veterans with PD, and will generate supporting data that will translate to more personalized and effective rehabilitation programs for people with PD.

## List of Abbreviations

Provide a list of all abbreviations used in the protocol and their associated meanings.

PD- Parkinson's Disease

APOE- Apolipoprotein E

BDNF- Brain-Derived Neurotrophic Factor

AD- Alzheimer Disease

VHA- Veterans Health Administration

NCI- No Cognitive Impairment

MCI- Mild Cognitive Impairment

PD-D- Parkinson's Disease Dementia

MDS-UPDRS- Movement Disorders Society Unified Parkinson's Disease Rating Scale

MoCA- Montreal Cognitive Assessment

WPDR- Washington Parkinson State Registry

## **2.0 Introduction**

Parkinson's disease (PD) is the second most common neurodegenerative disease, behind Alzheimer's disease (AD). Over 4 million people worldwide are diagnosed with PD (1, 2) and its prevalence is expected to double by 2030, when it is estimated that more than 1 million Americans will carry a diagnosis of PD. Since 2010, PD is recognized by the Department of Veterans Affairs as a service connected condition, associated with exposure to Agent Orange or other herbicides during military service, affecting approximately 80,000 United States Veterans. **Gait impairment and increased risk of falls in PD.** Gait disturbance is one of the most consequential motor symptoms experienced by individuals with PD, contributing to increased risk

of falls (3), and resulting in increased disability (4), reduced quality of life (5), and increased caregiver burden (6). The impact of gait impairment on people with PD, their caregivers, and the healthcare system make gait a critical therapeutic target. Although gait impairment is not typically a presenting sign, its prevalence increases with disease progression. Within 3 years of diagnosis, over 85% of people with PD develop gait problems (7). Unfortunately, this debilitating symptom remains difficult to treat. Typical gait abnormalities include reduced speed, shortened step length, and increased stride-to-stride variability. Gait impairment worsens with disease progression, when festination and freezing can emerge, contributing to an increased risk for falls (3).

Falls while walking and their associated morbidity and mortality present a significant and growing challenge at both individual and societal levels (8, 9). The diagnosis of PD contributes to more falls than any other chronic disease and imposes a heavy burden in people over 65 years (10). Healthcare for fall-related injuries has a significant impact on the provision of care within the Veterans Health Administration (VHA). Administrative data from 1997 through 2001 indicate that over 60,000 unique patients received services for fall-related injuries, with over 20,000 patients receiving care for fall-related injuries in 2001 alone (11). Within the VHA alone, the annual cost of the initial outpatient visits associated with fall-related injuries was estimated at nearly 3.3 million dollars (11). Acknowledging this important issue, the VA's National Center for Patient Safety worked with the Veterans Integrated Service Network 8 Patient Safety Center of Inquiry (VISN 8 PSCI) and others to develop a toolkit designed to aid facilities to develop comprehensive fall and injury prevention programs (12).

**Cognitive impairment in PD.** Although PD was once considered a disorder of movement alone, cognitive impairment is now recognized as a common and consequential non-motor feature of the disease (13). People with PD can be classified as having no cognitive impairment (PD-NCI), mild cognitive impairment (PD-MCI), or dementia (PD-D) based on neuropsychological assessment and the impact on functional independence (13, 14). Similarly to gait impairment, cognitive impairment is very prevalent in people with PD. PD-MCI is present in approximately 25% of PD patients at the time of diagnosis, with an estimated cross-sectional prevalence of up to 60% (14, 15). Nearly 80% develop dementia during the course of the disease (16). PD is associated with deficits in executive function, attention, memory, language, and visuospatial abilities (13).

Interestingly, associations between cognition and gait have been demonstrated among older adults with and without cognitive impairment, and the combination of cognitive and gait impairments may accelerate functional decline (17, 18). In PD, gait disturbance is associated with cognitive impairment; for example there is a higher prevalence of falls among PD patients with cognitive impairment compared to those without cognitive impairment. Also, deficits in both global cognition and specific executive functions (processing speed) in patients with PD have been consistently associated with more severe postural instability and gait abnormalities, as measured by composite scores from the Unified Parkinson's Disease Rating Scale (UPDRS) (23). Together, these studies demonstrate a complex pattern of associations between gait impairment and specific cognitive domains. However, we have a limited understanding of the impact of cognitive dysfunction in PD on walking, particularly complex walking tasks that are critical to day-to-day mobility.

**Rehabilitation as treatment for gait and cognitive impairment in PD.** Since gait impairment in PD is typically minimally responsive to other treatments, rehabilitation is a critical part of its clinical management. While gait impairment may be initially improved by pharmacological and surgical approaches, their efficacy declines with disease progression. Antiparkinsonian medications improve gait speed and stride length but have mixed effects on stride-to-stride variability, which has been associated with falls in PD (19, 20). In addition, medications do not reliably reduce festination and freezing of gait, which can emerge with disease progression. A recent systematic review demonstrated that physical therapy can improve walking in people with

PD (21). Two common approaches to gait training for people with PD are treadmill training and training with a cognitive cueing strategy, both of which can effectively improve gait in people with PD (21). Exercise programs involving walking have also been shown to improve cognition in older adults (22), and there is some early evidence to suggest that such programs may also improve cognition in PD (23-26). In particular, gait training programs that incorporate walking at moderate aerobic intensity have the potential to improve both gait and cognitive impairments in PD.

The capacity for learning is fundamental to successful rehabilitation. Learning, like memory, is often defined as either procedural or declarative in nature, though this distinction likely oversimplifies these complex processes. Procedural, or implicit, learning develops gradually through repetition, does not require conscious awareness, and is expressed through improved performance. Despite the proposed role of the basal ganglia in procedural motor learning, people with PD do demonstrate preserved acquisition and retention of procedural motor learning (27). Practice improves motor performance in people with PD (28). However, research from both upper extremity (29) and postural control tasks (30) suggests people with PD may require more practice than healthy individuals in order to achieve similar performance gains, consistent with reduced efficiency of learning. In contrast to procedural learning, declarative, or explicit, learning requires awareness and attention, and results in knowledge that can be consciously recalled and verbalized. Impairments in declarative learning have been demonstrated among people with PD during both cognitive (31) and motor tasks (32). Research suggests that both procedural and declarative learning are impaired in PD, and both types of learning may be more affected in people with PD who have cognitive impairments (33). Treadmill training is a form of gait rehabilitation that emphasizes procedural motor learning, while cognitive cueing emphasizes declarative motor learning (i.e., verbal instructions to focus on walking), thus we believe a combination of both strategies should be used when treating PD patients.

**Gap in knowledge to be addressed.** PD is a heterogeneous disorder with considerable inter-individual differences in clinical features, disease course, and treatment response, which can be due to disease processes and other clinical variables, but also by other factors such as genetics. Currently, rehabilitation approaches do not take into account an individual's genetic profile, which may impact learning and therefore mediate the response to rehabilitation. Two genes that have been shown to play an important role in motor learning are the genes coding for brain-derived neurotrophic factor (*BDNF*) and apolipoprotein E (*APOE*). The *BDNF* protein is involved in neuronal survival and synaptic plasticity (34) and a variant in the *BDNF* gene (Val66Met), carried by approximately 30% of European-Americans has been associated with greater error in motor learning in healthy individuals (35) and appears to impact rates of motor learning on a locomotor adaptation task in individuals with cerebrovascular accidents (36). This variant results in 18 to 30% less activity-dependent secretion of the *BDNF* protein (37). On the other hand, the *APOE* gene encodes a glycoprotein that plays an important role in neuronal repair and synaptic remodeling. Genetic variation in this gene (*APOE-ε4*) is a well-known risk factor for AD, but has also been associated with motor decline (explained mostly by a loss in muscle strength) (38) and abnormal gait (shorter stride length and greater dual-task related disturbances in stride length) (39), in the elderly. Recently, we and others have shown that the *APOE-ε4* allele is associated with poorer performance on specific cognitive domains in PD (40). Therefore, understanding the effect of genetic variants on the physical and cognitive improvement in response to training is an essential first step to investigate this relationship.

**Relevance of this project:**

Understanding the impact of these genetic variants on physical and cognitive improvements in response to gait rehabilitation is critical to personalize the rehabilitation prescription for patients with PD. Our long-term goal is to identify genetic subgroups of patients with PD with differential response to different rehabilitation approaches. If such subgroups exist, we can then target effective and personalized rehabilitation strategies to each subgroup.

A greater understanding of the benefits on gait and cognitive impairments after rehabilitation training, and how genetic variants may be involved in learning will not only help Veterans with PD, but will also inform our understanding of this relationship in Veteran populations that also experience both gait and cognitive impairment due to other neurologic diseases or injuries such as AD or traumatic brain injury respectively.

We are rapidly approaching an era when understanding the impact of genetic variations will help physical therapists and other rehabilitation professionals better identify individual differences in symptom manifestation, treatment response, and overall patient wellness. Providing better tools for stratifying individual patients will undoubtedly enhance the impact of rehabilitation.

### 3.0 Objectives

Parkinson's disease (PD) is a heterogeneous neurodegenerative condition that currently affects over 4 million people worldwide and, as a service connected condition, affects approximately 80,000 United States Veterans (2, 41, 42). Gait impairment is common in patients with PD, resulting in increased disability (4), reduced quality of life (5), and increased risk of falls (3). As PD progresses, gait impairment is typically minimally responsive to pharmacological or surgical interventions, making rehabilitation an essential aspect of clinical care in this patient population. Physical therapy is a key component of the rehabilitation process; specifically gait training on a treadmill results in short-term improvement in gait speed and physical endurance in PD (21). It is well-known that patient responses to rehabilitation interventions are variable despite apparent similarities in impairment profiles (21). An important factor that could impact the outcome of rehabilitation is cognitive function. Cognitive impairment, often underdiagnosed, is also a very common symptom and has been shown to affect mobility in PD (10). In many patients with PD, numerous aspects of learning, including motor learning, are impaired, suggesting that one factor contributing to variable rehabilitation response is the ability to consistently learn and implement learning-related changes in order to gain and sustain gait improvements. We believe that those Veterans with learning impairments may not receive as much benefit from routine gait rehabilitation and, if this is true, we may need to develop and tailor training programs to specifically target these individuals. We believe that the inter-individual heterogeneity in treatment response in PD can be explained not only by disease process and other clinical variables, but also by an impact from genetic factors. Increasing evidence suggests genetic variation is associated with brain plasticity and motor learning (35, 38); thus studying these genetic factors may help to differentiate subsets of Veterans with PD based on their response to rehabilitation and therefore identify optimal rehabilitation approaches for each subgroup. The proposed work will focus on variants in two genes (the *APOE-ε4* and *BDNF-Met66* alleles), which are postulated to play important roles in cortical plasticity and neural repair, thus having an effect on learning and cognition. We aim to understand whether genetic variants in these genes are associated with motor and cognitive outcomes in response to gait rehabilitation in Veterans with PD. **We hypothesize that Veterans with PD who carry an *APOE-ε4* or *BDNF-Met66* allele will demonstrate smaller improvements in gait (Aim 1) and cognition (Aim 2) during/after a 10-week gait treadmill-training program.** We will test these hypotheses through the following specific aims:

**SPECIFIC AIM 1: Determine the effect of genotype on motor learning in response to gait rehabilitation among Veterans with PD.** Aim 1 is designed to test the hypothesis that motor learning is reduced in those carrying *APOE-ε4* or *BDNF-Met66*. We will compare the effect of a 10-week gait treadmill-training program on motor learning, defined as increased walking speed from pre-training (0 weeks) to 2 weeks into training and to post-training (10 weeks), between the three genotype groups. Secondary hypotheses will determine the effect of genotype on: (1) the retention of motor learning changes (from post-training (10 weeks) to follow-up (16

weeks)); and (2) the transfer of motor learning from the trained walking task (straight line walking at a self-selected speed) to more complex walking tasks (dual-task walking and turning while walking) from pre-training to post-training..

**SPECIFIC AIM 2: Determine the effect of genotype on cognitive changes in response to gait rehabilitation among Veterans with PD.** We will compare the effect of a 10-week gait treadmill-training program on cognition in each of the three genotype groups. Changes in cognition will be assessed by comparing performance on cognitive tests from pre-training (0 weeks) to post-training (10 weeks).

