Objective spatiotemporal parameters of walking will be measured with the portable APDM Movement Monitoring Solutions system (APDM, Inc.), which uses six inertial sensors attached to the wrists, feet, pelvis, and trunk to quantify body movements during mobility tasks. We have used the APDM inertial sensor system extensively to quantify balance and gait in people with PD and other older adult populations, with data collection completed for >20 people with PD and >90 people with mild cognitive impairment or early AD. Participants will walk back and forth across a 7-m course for one minute. Two trials each will be performed under single-task (walking only) and dual-task walking (walking while performing serial-3 subtractions), allowing us to quantify changes in both straight-line walking and 180 degree turns under conditions of increasing cognitive load. Motor learning will be assessed using the primary outcome of gait speed during straight-line walking under single-task conditions. Therapists will be blinded to the subjects' genotyping status.

**Secondary analyses:** We will also measure retention and transfer of motor learning. Retention of motor learning will be assessed by differences in walking speed from post-training (10 weeks) to follow-up (16 weeks) time points (**Table 1**). Transfer of motor learning from a simple walking task (self-paced straight-line walking on a treadmill) to complex walking tasks (turning, dual-task walking) that are commonly impacted by PD will be assessed by the change in walking speed during complex walking tasks from pre-training to post-training time points.

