## 5.6 Data Analysis

Descriptive analyses at baseline will be used to examine participant characteristics and demographic variables and compare them across the sample and by genotype, including age, sex, height, education, disease duration, disease severity, physical activity levels cognitive task performance and global cognition. Histogram and quantile-quantile plots will be generated for each variable and transformation will be used when necessary to improve the fit to normality.

**Aim 1:** The primary hypothesis that motor learning is reduced in those carrying *APOE* or *BDNF* genetic variants compared to those without *APOE*-ε4 or *BDNF*-Met66 genotypes will be tested using repeated-measures analysis of variance (ANOVA) with one within-group factor, time point (0 weeks, 2 weeks for short-term motor learning; 0 weeks, 10 weeks for long-term motor learning) and one between-group factor, genetic group (*BDNF*-Met66 group, *APOE*-ε4 group, no Met66 nor ε4 allele group) to examine changes in the primary outcome measure for walking, gait speed. The secondary hypothesis examining the effect of genotype on retention of motor learning changes will be tested using repeated-measures ANOVA with one within-group factor, time point (10 weeks, 16 weeks follow-up) and one between-group factor, genetic group to examine changes in gait speed. The secondary hypothesis examining the effect of genotype on the transfer of motor learning from the trained walking task (straight line walking at a self-selected speed) to more complex walking tasks will be tested using repeated-measures ANOVA with one within-group factor, time point (0 weeks, 10 weeks) and one between-group factor, genetic group to examine changes in gait speed for dual-task walking and peak turning velocity for turning while walking. For all analysis, unadjusted models will be used. We will consider adjusting for age, height, cognitive task performance (for dual-task) or global cognition if any of these factors are shown to be different between genotype groups.

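### Retention is tested only as the absolute week 10-16 change in gait speed, so if loss depends on the gain, the contrast tends to favour groups that learned less

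*Combined protocol and SAP*

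**What the plan says.** Section 3.0, Specific Aim 1, treats motor learning as a rise from baseline, "defined as increased walking speed from pre-training (0 weeks) to 2 weeks into training and to post-training (10 weeks". The overall hypothesis there is that carriers of either allele "will demonstrate smaller improvements in gait (Aim 1) and cognition (Aim 2".

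Retention is then a secondary hypothesis, on the effect of genotype on "the retention of motor learning changes (from post-training (10 weeks) to follow-up". Section 5.5 (Secondary analyses) says "Retention of motor learning will be assessed by differences in walking speed from post-training (10 weeks) to follow-up (16 weeks) time points". Section 5.6 says that "retention of motor learning changes will be tested using repeated-measures ANOVA with one within-group factor, time point (10 weeks, 16 weeks follow-up", with genetic group as the between-group factor and gait speed as the outcome.

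On covariates, Section 5.6 says "For all analysis, unadjusted models will be used", and then "We will consider adjusting for age, height, cognitive task performance (for dual-task) or global cognition" if these differ between genotype groups. Neither baseline speed nor the week 0-10 gain is on that list. Table 1 shows gait assessed at weeks 0, 2, 10 and 16. No week 0-16 contrast and no share of the gain retained is planned.

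**The concern.** What is to be retained is the rise in speed from week 0, but the retention test never uses week 0. It compares only the metres per second lost after training stops. A group that gained little has little training gain to lose, so a small loss can mean either that learning was well kept or that there was not much of it. The plan gives no means of telling these apart in the retention analysis.

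The primary hypothesis predicts this situation, with smaller gains in carriers. Section 5.2 (Payment) calls the duration of the benefit a very important question and pays most for the week 16 visit for that reason. The Introduction wants genetic subgroups identified so that rehabilitation can be tailored. A finding that carriers hold their training as well as or better than others, arising only because they gained less, would mislead that aim.

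**Working it through.** **Inputs from the documents.** Three groups of 10 (Section 5.1), two time points (10 and 16 weeks) and an unadjusted repeated-measures ANOVA (Section 5.6). The documents give no expected gain, SD, alpha or share retained, so there is no stated figure to reproduce.

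**Assumptions.** Two-sided 5% level; week 0-10 gain 0.10 m/s in non-carriers and 0.05 m/s in each carrier group; SD of the week 10-16 change 0.05 or 0.08 m/s. Results below are given as SD 0.05 / SD 0.08.

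**Step 1: what the test compares.** With two time points, the group x time test is the same as a one-way ANOVA on the change score. If a group keeps a share r of its gain,

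expected loss = (1 - r) x gain.

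For equal r below 100%, a smaller gain always gives a smaller loss.

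**Step 2: every group keeps 50%.** Losses are 0.5 x 0.10 = 0.05 m/s in non-carriers and 0.5 x 0.05 = 0.025 m/s in carriers, a contrast of 0.025 m/s in the carriers' favour.

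- Pooled carriers (20) against non-carriers (10): SE = SD x sqrt(1/20 + 1/10) = 0.0194 / 0.0310. So z = 0.025/SE = 1.29 / 0.81, and carriers are seen to lose less in 90% / 79% of trials.
- Three-group F test: the mean change is -0.0333, the deviations are -0.0167, 0.0083 and 0.0083, and their squares sum to 0.000417. Noncentrality = 10 x 0.000417 / SD² = 1.67 / 0.65. On 2 and 27 df, p<0.05 in 18% / 10% of trials.

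**Step 3: carriers keep a smaller share.** If non-carriers keep 70% and carriers 40%, losses are 0.3 x 0.10 = 0.03 and 0.6 x 0.05 = 0.03 m/s. The expected losses are equal and the test rejects in about 5% of trials, so the difference in share is invisible to it.

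**Step 4: a different error model.** A separate simulation used gains varying between people (SD 0.05) and error SD per assessment of 0.03 or 0.05 m/s. With gains of 0.15 v 0.05 m/s and 50% kept, losses are 0.075 v 0.025 m/s. Carriers look better in 99.5% / 95.7% of trials and p<0.05 occurs in 59% / 29%. On the same scenario the week 0-16 net gain is 0.075 v 0.025 m/s (carriers worse by 0.05 m/s) and the shares are equal.

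**Step 5: when there is no bias.** With equal gains and equal shares the test rejects in about 5% of trials with no preferred direction. If all groups lose a common absolute amount, or nothing is lost, the expected contrast is zero whatever the gains were.

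**Step 6: can a retained share be the test?** The share is the week 0-16 gain divided by the week 0-10 gain. For one carrier group of 10 with a 0.05 m/s gain, half of it kept and independent visit errors, the bootstrap 95% interval is typically about -0.1 to 1.1 / -1.3 to 2.3. The interval for the difference in share from non-carriers is about 1.4 / 4.0 wide. The gain itself has an interval excluding zero in only about 80% / 42% of trials.

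**The case against.** The plan is consistent: the objectives, evaluations and analysis sections all use the same week 10-16 contrast, which is a conventional way to ask whether speed is held once training stops. The documents never define retention as a proportion, and speed held in m/s is a fair reading of how long the benefit lasts. The primary result on the gain will be reported for the same groups, so a careful reader could put the two together. This stands as a defence of the week 10-16 test as a quantity worth having. It does not supply a planned analysis or rule that links the loss to the gain.

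A reader might infer that the trial will declare carriers better retainers, or that the test has the wrong null. The documents support neither. The retention hypothesis has no stated direction, no interpretation rule is given, and the bias needs loss to depend on the gain. A common loss, for example from progression over the six weeks, would leave the contrast unbiased, and a share would then make the low-gain group look worse. Under the main assumptions a significant result is also absent in 82% to 90% of trials.

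A reader might also infer that a retained share should replace the test. Step 6 shows that it is too imprecise with 10 per group, especially in the low-gain groups.

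**Conclusion.** The concern holds as a conditional one. The planned retention analysis ignores the week 0-10 gain. If loss scales with or is limited by the gain, and carriers gain less as hypothesised, the contrast tends to favour carriers when all groups keep the same share, and it can miss a smaller share kept. Under the main assumptions the estimate favours carriers in 90% to 79% of trials and is significant in 18% to 10% instead of 5%. These sizes rest wholly on assumed gains, shares and SDs.

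The matter concerns a secondary hypothesis. It is worth correcting because the problem arises in the scenario the trial expects and the remedy is nearly free. The week 0-16 contrast alone would not settle it either, since that mixes how much was learned with how much was kept. The gain, the loss and the net gain have to be read together.

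**What to change.** In Sections 5.5 and 5.6:

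1. Keep the week 10-16 group x time test, but label it *loss after training*.
2. Fit weeks 0, 10 and 16 in one model. Report the week 0-10 gain, the week 10-16 loss and the week 0-16 net retained gain side by side, for each group and as carrier minus non-carrier contrasts, with 95% confidence intervals.
3. State that a smaller or equal week 10-16 loss in a group with a smaller week 0-10 gain will not by itself be reported as better or equal retention.
4. Optionally show the group-level retained share with its interval where the gain is clearly above zero, as description only and not as the retention test.

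The cost is wording and a few lines of code on data already collected, one more contrast, and a more cautious conclusion about retention.
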